2.8.1.3 Adverse events by subgroup

Incidences of TEAE will be displayed by the following subgroup.

- Age (< 40 or >= 40)
- Gender
- Region (Japan or non-Japan)

This analysis will be performed for Cut-off 1 and Cut-off 2 analyses.

In addition, for Cut-off 2 analysis only, the following subgroup analyses will be provided:

- Incidence of TEAE by region and CTCAE grade
- Incidence of TEAE will be displayed by subgroup defined on basis of whether each patient had home-injection during the treatment period.

2.8.1.4 Impact assessment of potential unblinding

Incidence of the TEAEs will be summarized by subgroup defined by impact of potential unblinding.

This analysis will be performed only for Cut-off 1 analysis.

2.8.2 Deaths

Death, if any, will be listed by treatment group. All deaths as recorded in the database will be included at each analysis cut-off.

2.8.3 Laboratory data

Data summaries will be provided in SI units. The summary of laboratory evaluations will be presented for 3 groups of laboratory tests: Hematology, Chemistry and Urinalysis. Subgroup analyses as specified in [Section 2.2.1](#) will be performed as needed.

Laboratory data will be summarized by presenting summary statistics (mean, median, standard deviation, Min and Max) of raw data and change from baseline values to each study visit-window by treatment group, and by presenting shift tables using clinically notable ranges (baseline to most extreme post-baseline value) by treatment group. Change from baseline (i.e. post baseline value – baseline value) will only be summarized for patients with both baseline and post baseline values. Laboratory data, and specifically liver enzymes, will also be summarized by maximum change from baseline.

The number and percentage of patients with new or worsening laboratory abnormalities based on CTCAE grade (Section [5.3.4](#)) in each visit-window and at any time post baseline will be presented. Patients with specific laboratory abnormalities (defined by CTCAE grade 3 and 4) will be listed.

For liver enzymes, the number of subjects with newly occurring liver enzymes abnormalities will be summarized by treatment group. Newly occurring liver enzymes abnormalities are defined relative to the upper limit of normal (Section [5.3.2](#)).

Liver function test will also be presented graphically as matrix plots of each of the parameters (ALT, AST, TBIL, ALP) maximum post-baseline/ULN normalized.

For the shift tables, abnormalities based on CTCAE grades tables and liver frequency distribution tables, all applicable post-baseline values will be checked against the respective criteria and the rules for handling multiple laboratory assessments within visit windows will not be applied.

For continuous variables databased as <lower limit, these will be imputed as being half of the lower limit.

Regarding renal function, the overall frequency of events and percentage of patients with renal events during the treatment period will be summarized and detailed listings provided. Renal events will be defined in section [5.3.3](#).

The following analyses will be repeated for Cut-off 2 analysis:

- New or worsening abnormalities based on CTCAE grade

- New or worsening liver enzyme abnormalities at any time post-baseline
- Shift table
- Renal events
- Summary statistics

2.8.3.1 Serology at screening

Laboratory serology to determine patient's eligibility includes parameters with respect to hepatitis and HIV viruses, syphilis (RPR), and tuberculosis. Parameters with respect to hepatitis include 1) anti-hepatitis A virus IgM; 2) hepatitis B surface antigen and anti-hepatitis B core IgM/IgG antibody; 3) anti-hepatitis C virus IgG; 4) anti-hepatitis E virus IgM.

The result of each serology parameter is a categorical value. The number and percentage of patients with values in each of the categories will be provided by treatment group for all above-mentioned parameters. Serology test should be performed once at screening. For patients with multiple assessments, the latest result will be used in the summary. Additional serology data with numerical values may be collected but will not be reported.

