10. Patients at risk of developing or having reactivation of hepatitis: Positive results at Screening for serological markers for hepatitis (H) A, B, C, and E as below:

- anti-HA Immunoglobulin (Ig) M (IgM)
- HBs antigen positive or HBc IgM/IgG antibody positive, regardless of HBV DNA testing result
- HBs antibody positive and other HBV parameters negative (HBs antigen negative and HBc IgM/IgG antibody negative) without known history of anti-HBV immunization
- anti-HC IgG (if positive IgG, Hepatitis C Virus (HCV)-ribonucleic acid (RNA) polymerase chain reaction (PCR) will be performed and if negative, patient can be randomized)
- anti-HE IgM (if positive IgG and/or IgM, perform HE-RNA PCR and if negative, patient can be randomized)

NOTE: If the Investigator suspects false positive hepatitis serology results, such as an antibody pattern indicating acute hepatitis infection but no corresponding elevated liver enzymes and no signs or symptoms of liver disease, an infectious disease expert may be consulted. If the infectious disease expert finds no evidence of acute or chronic hepatitis infection and considers the serology results false positive and not clinically relevant, the Investigator must document (in source data) that the serology results are considered false positive and may then randomize the patient.

11. Have received any live or live-attenuated vaccines (including for varicella-zoster virus or measles) within 2 months prior to randomization

12. Have been treated with any of the medications listed below:

Medication	Exclusionary if used/used within required wash-out period
Systemic corticosteroids, adrenocorticotropic hormone	30 days prior to Screening MRI scan
Dimethyl fumarate	1 month prior to randomization
Intravenous immunoglobulin, plasmapheresis, fingolimod	2 months prior to randomization
Daclizumab	4 months prior to randomization
Teriflunomide	3.5 months prior to randomization or 1 month prior to randomization if patient undergoes accelerated elimination procedure and has documented teriflunomide plasma level below 0.02 mg/L before randomization
Natalizumab Mildly to moderately immunosuppressive/chemotherapeutic medications (e.g. azathioprine, methotrexate)	6 months prior to randomization

Medication	Exclusionary if used/used within required wash-out period

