The MRI technician will be responsible for:

- Familiarization with the MRI manual procedures and the study specific MRI protocol
- Performance of a "dry" or "dummy" run using the MRI parameters outlined by the MRI protocol
- Performance of high-quality MRI scans using the study specific parameters stored in the designated MRI scanner for the duration of the study
- Submission of the MRIs in the appropriate format to the central MRI reader immediately upon completion

Radiologist/Neurologist

The local radiologist/Neurologist will be responsible for:

- Reviewing each MRI scan performed for the study patients and contacting the Investigator in case of unexpected or safety-related findings detected on the MRI scan

6 Visit schedule and assessments

[Table 6-1](#) lists all of the assessments and indicates with an "x" when the visits are performed.

Patients should be seen for all visits on the designated day per the schedule of assessments, or as close to it as possible within the visit windows. Missed or rescheduled visits should not lead to automatic discontinuation.

In case a visit is performed outside the schedule, subsequent visits shall be performed in keeping with the original visit schedule (one month is defined as 28 calendar days). In addition to the planned visits, patients may have unplanned visits due to a MS relapse, an acute illness of undetermined cause, for other reasons, or at the discretion of the Investigator. Data collected during unplanned visits will be recorded in the unplanned visit CRFs.

At Week 24, all assessments required for the Core part MUST be completed prior to the first study drug administration for the Extension part.

In the Extension part, patients will be asked to complete a diary to record information pertinent to study drug administration (including date and time of sc injections) and home pregnancy testing (date and results) for females of childbearing potential. The patient is requested to bring the completed diaries with them to each visit and the Investigator/Study Nurse/Study Coordinator must review these for completeness and for potential AEs, injection related reactions, study drug interruptions etc. and record information obtained from the diaries on the relevant CRFs.

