Visit		SCR (D-45 to D-8)	BL (D-7 to D1 (pre-treatment)	D1 ¹	D2	D5	D7	D14	W4 (D28)	W8	W12	W16	W20	W24		W25 ¹⁹	W26 ¹⁹	W28	W36	W48	W60 ²⁰	W72 ²⁰
Visit No.	1	20	110	120	130	140	150	160	170	180	190	200	210	220	230	240	250	260	270	280	1999	
Visit Window (days)	n.a.	n.a.	n.a.	0	-1	±1	±1	±3	±7	±7	±7	±7	±7	±1	±1	±3	±7	±7	±14	±14	n.a.	
Contraception status ¹¹	X	X						X	X	X	X	X	X			X	X	X	X	X	X	
PK sampling ¹²		X		X	X	X	X	X		X			X			X	X	X	X	X	X	
ADA sampling ¹²		X						X		X			X			X	X	X	X	X	X	
Total IgM, IgG levels	X ^{9a}	X ^{9a}						X		X			X			X	X	X	X	X	X	
Serological markers for hepatitis A, B, C, and E	X												X									
HIV test	X																					
MRI ¹³	X									X	X	X	X				X	X			X ¹⁴	
EDSS	X	X ^{9b}	X ^{9b}						X		X						X	X	X	X	X	
eCSSRS	X ^{9a}	X ^{9a}	X	X	X	X	X	X	X	X	X	X	X	X	X	X	X	X	X	X	X	
AEs	X	X	X	X	X	X	X	X	X	X	X	X	X	X	X	X	X	X	X	X	X	
MS Relapse	X	X	X	X	X	X	X	X	X	X	X	X	X	X	X	X	X	X	X	X	X	
Prior/Con Meds ¹⁵	X	X	X	X	X	X	X	X	X	X	X	X	X	X	X	X	X	X	X	X	X	
Phone interview ¹⁶															X	X	monthly between planned visits					
Patient diary review															X	X	X	X	X	X	X	
Disposition														X								X

A/A=Acetaminophen/Antihistamine; ADA=Anti-drug-antibody; AEs=Averse events; BL=baseline; Con meds=Concomitant medications; D=day; Excl.=exclusion; Incl.=inclusion; n.a.=not applicable; S= Steroid; SCR=screening; W=week.

1. Randomization and first dose (usually expected on the same day). If first dose occurs on a different day after randomization, the day of first dose should be considered to be Day 1. Patients must remain at the site under observation for a minimum of 5 hours following dosing on Day 1.
2. EOS visit will be required for all patients (Patients who permanently discontinue study drug and patients who complete the study).
3. Syphilis and Tuberculosis testing must be done as part of eligibility check (Exclusion criterion #9) unless completed in the last 6 months prior to screening with documented negative results. For syphilis testing, it should be done per local clinical practice (e.g. by positive RPR). For tuberculosis testing, QuantiFERON®-TB Gold test will be done by the central laboratory to assess patient's eligibility at Screening.
4. All assessments required for the Core part MUST be completed before the patient receives the first dose for the Extension part at Week 24. Patients must remain at the site under observation for a minimum of 5 hours following dosing at Week 24.

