15.2 Guidance on monitoring of patients with infections

All infections that develop during the study will be reported as AEs on the appropriate eCRF capturing AEs. Treatment and additional evaluations will be performed at discretion of the Investigator.

The Investigator should remind the patient of the risk of infections and instruct them to promptly report any symptoms of infections to the Investigator. The patients must also be reminded to always carry their Patient Information Card (with site contact information and which identifies them as participants in a clinical study with investigational and control agents with potential immunosuppressive effects) and to show this to any local healthcare provider they may consult and ask that the Investigator be contacted.

In the case of suspected or confirmed serious (CTCAE, Grade 3-4) or atypical infection, study drug interruption should be considered. The Investigator should inform the Sponsor Medical Advisor of any such cases.

When evaluating a patient with a suspected infection, the most sensitive tests available should be used (i.e. that directly detect the pathogen, as with PCR).

The Investigator should consider early treatment with specific antimicrobial therapy on the basis of clinical diagnosis or suspicion thereof in consultation with infectious disease experts, as appropriate. The Investigator should inform the Sponsor Medical Advisor of any such cases.

Investigators should consider the added immunosuppressive effects of corticosteroid therapy for treatment of MS attack/relapse and increase vigilance regarding infections during such therapy and in the weeks following administration.

In oncology patients treated with ofatumumab, cases of fatal HBV reactivation and fatal infection due to hepatitis B in patients who have not been previously infected have occurred (refer to local ARZERRA® prescribing information). This study excludes the patients who are at potential risk of HBV reactivation (See [Section 4.2](#) Exclusion criterion 10). In patients with suspicion of HBV infection during the study, laboratory testing for HBV should be done. For patients who show new evidence of HBV infection [HBs antigen positive (regardless of antibody status) or HBs antigen negative but HBc IgM/IgG antibody positive], the Investigator is advised to consult with physicians with expertise in managing hepatitis B regarding monitoring and consideration for HBV antiviral therapy.

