These patients will be followed for a total of at least 36 weeks after study drug discontinuation (by 36 weeks the majority of patients are expected to have repleted their circulating B-cells, see Protocol Section 3.3).

A longer than 36 weeks of post-treatment Safety FU period will be required for patients who have not repleted their B-cells (i.e. B-cells not back to baseline value or to lower limit of normal (LLN) whichever comes first as determined by central lab) at 36 weeks.

These patients will continue to be followed with assessments every 12 weeks until their B-cell counts have repleted. To protect the study blind, the assessment of B-cell counts will be performed centrally and the Investigators and Sponsor study team will only be informed of whether or not continued follow-up is necessary.

Patients who have initiated therapy with another disease modifying/immunosuppressive therapy before the end of the 36-week follow-up will not be monitored beyond 36 weeks.

Figure 1-1 Study design

* Patients randomized to placebo in the Double-blind treatment period will receive ofatumumab 20 mg sc at Week 24, 25 and 26 as loading dose regimen. Patients randomized to ofatumumab in the Double-blind treatment period will receive ofatumumab 20 mg sc at Week 24 and the matching placebo sc at Week 25 and 26. In all patients, the extension part starts with the Week 24 injection.

** Patients who prematurely discontinue study drug or patients who do not enter the umbrella extension study will enter the Safety FU period following their EOS visits.

*** Umbrella extension study (planned) will be conducted under separate protocol.

Data cut-off 1 is defined as the date the last patient completes all the assessments for Week 24.

Data cut-off 2 is defined as the date the last patient completes all the assessments for Week 48.

Three types of analyses to be conducted are described in the SAP. They will be referred to in this document as Cut-off 1 analysis, Cut-off 2 analysis, and EOS analysis:

1. The Cut-off 1 analysis will be conducted for the Core part. Data up to the Week 24 (cut-off 1) will be used. Data from the safety FU period for patients who prematurely discontinued from study treatment before Week 24 will also be included. The analysis will be performed when the last patient has completed the double-blind loading dose period at Week 28. This analysis will be used in support of the registration of ofatumumab in Japan.

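### The screening serology rule in SAP 2.8.3.1 has no pre-dose limit, although Table 6-1 schedules a second hepatitis test, and no by-arm serology summary is specified for post-screening results

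*SAP*

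**What the plan says.** SAP 2.8.3.1 is headed as serology at screening and opens with its purpose: "Laboratory serology to determine patient's eligibility includes parameters with respect to hepatitis and HIV viruses, syphilis (RPR), and tuberculosis". It then states "Serology test should be performed once at screening" and adds "For patients with multiple assessments, the latest result will be used in the summary". The hepatitis parameters it lists are anti-HAV IgM, HBs antigen, HBc antibody, anti-HCV IgG and anti-HEV IgM. HBs antibody is not listed, although exclusion criterion 10 in Protocol 4.2 uses it ("HBs antibody positive and other HBV parameters negative", without known immunization).

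In Protocol Table 6-1 the row "Serological markers for hepatitis A, B, C, and E" carries two marks, Screening and a later visit. The HIV row beneath it carries one. Protocol 6.5.4.4 describes hepatitis testing at Screening only.

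On timing, Protocol Section 6 says: "At Week 24, all assessments required for the Core part MUST be completed prior to the first study drug administration for the Extension part". On the Cut-off 1 analysis, SAP 1.1 says: "Data up to the Week 24 (cut-off 1) will be used".

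**The concern.** A table meant to show eligibility should hold pre-treatment values. The rule in 2.8.3.1 does not say so, and the schedule provides a later value that a literal programmer would pick. The SAP already has a suitable definition in 2.1.1 (last non-missing result on or before the first date of study drug), but 2.8.3.1 does not refer to it.

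The later value also matters as safety data. Protocol 15.2 reports "cases of fatal HBV reactivation and fatal infection due to hepatitis B" in oncology patients given ofatumumab, and it defines new evidence of HBV infection during the study by serology: HBs antigen or HBc antibody positivity. Both markers belong to the repeated panel as SAP 2.8.3.1 lists it. Because Core part assessments at Week 24 precede the first Extension dose, a Week 24 sample would compare ofatumumab with placebo before the placebo patients switch. The SAP specifies no count of patients who become positive.

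**Working it through.** The plan states no figure on this point, so the check sets the texts side by side and counts the patients exposed to the rule.

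**1. Where the second mark falls.** Table 6-1 has 21 visit columns, confirmed by the 21 entries in its visit-number row. Counting cell positions in the extracted text:
- Hepatitis serology: columns 1 and 13, i.e. Screening and Week 24.
- HIV: column 1, Screening only.
- MRI, as an alignment check: Screening, Weeks 12, 16, 20, 24, 36, 48 and EOS. The Core part weeks match the primary endpoint, and all the weeks match SAP Table 2-1.
- Not every row aligns. EDSS falls on Weeks 8 and 16, where SAP Table 2-2 has Weeks 12 and 24. ECG falls on Weeks 25 and 72 among others, where Protocol 6.5.5 gives Screening, Week 24, Week 48 and EOS.

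A second hepatitis mark after Screening is therefore clear. Week 24 is its likely position but is not confirmed by running text.

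**2. Patients exposed to the rule.** Inputs are 60 patients randomized 2:1 and 10% dropout (SAP Section 3). Equal dropout by arm is an assumption.
- All patients: 60 × 0.90 = 54
- Ofatumumab: 40 × 0.90 = 36
- Placebo: 20 × 0.90 = 18

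**3. The two readings of the rule.**

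| Reading | Screening hepatitis results replaced | What happens to the post-screening results |
|---|---|---|
| Literal: latest result of any date up to the cut-off | up to about 54 of 60 | shown as if they were screening results |
| Narrow: latest of the screening retests | 0 of 60 | no specified serology summary |

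Only the hepatitis markers are exposed. No later HIV, syphilis or tuberculosis test is scheduled.

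**4. Whether another section covers the later results.** SAP 2.8.3 covers hematology, chemistry and urinalysis. SAP 2.8.3.2 names pregnancy tests, B- and T-cell counts and immunoglobulins. Neither Table 5-2 nor the legible visit-window tables in 2.1.2.1 list a hepatitis marker. The general sentence in SAP 2.8, that safety assessments are summarized or listed as appropriate, specifies no output.

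**5. What one unreported conversion would represent.** With x = 1 and n = 36, the proportion is 1/36 = 2.8%. The exact (Clopper-Pearson) limits are:
- Lower: 1 − 0.975^(1/36) = 0.07%, rounded to 0.1%
- Upper: the 0.975 quantile of Beta(2, 35) = 14.5%

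The single case is hypothetical. It shows how much one patient weighs in a trial of this size.

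**The case against.** The best defence is that the rule is sound for its stated purpose. The heading and opening sentence confine the table to screening, and the protocol allows retests before randomization (the note closing Section 4.2, and the repeat QuantiFERON test in criterion 9). On that reading the latest retest is the qualifying one and nothing is overwritten. This stands as a possible reading. It does not close the gap, because the post-screening hepatitis results then have no specified summary.

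Three stronger inferences are tempting, and the documents do not support them.

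- *That screening results will certainly be overwritten.* The text permits this but does not compel it.
- *That new hepatitis cannot show up by arm.* Protocol 15.2 has all infections reported as adverse events, and SAP 2.8.1 tabulates TEAEs by arm, including those leading to discontinuation. The hepatic SMQ and liver-enzyme tables add coverage. What remains open is the asymptomatic seroconversion. Under Protocol 7.1 an abnormal test result is an adverse event only if it causes signs or symptoms, is considered clinically significant or requires therapy, so reporting can turn on the investigator's judgment.
- *That a positive entry would be a false eligibility failure.* Criterion 10 admits some positives: anti-HCV or HEV antibody with negative PCR, and results that an expert judges to be false positive. SAP Tables 5-4 and 5-5 assign analysis sets from listed deviations and other criteria, none of which is a hepatitis serology result, so no analysis population changes.

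It is also fair to object that HBs antibody is a poor conversion marker. Protocol 15.3 says hepatitis B vaccination should be considered before treatment in patients at risk, and a vaccine response would look like a conversion.

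**Conclusion.** The concern holds as an inconsistency between the SAP and the schedule, with a limited reporting gap. SAP 2.8.3.1 assumes one test while Table 6-1 schedules two, and neither reading of its rule gives a satisfactory result: one puts on-treatment values into an eligibility table, and the other leaves those values without a by-arm summary. The replacement count of about 54 is an upper figure. It rests on the literal reading, on Week 24 being the second visit, and on 10% dropout. The safety gap is confined to seroconversions not reported as adverse events. The efficacy analyses and the analysis populations are not affected.

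**What to change.** 1. In SAP 2.8.3.1, use the last result on or before the first dose of randomized treatment in the Core part. The phrase should name the Core part, because SAP 2.1.1 redefines the first date of study drug as the first ofatumumab dose for the Cut-off 2 and final safety analyses.
2. Add to the Cut-off 1 safety outputs, on the SAF by treatment received, a shift table from the pre-dose result to post-screening results (scheduled and unscheduled) for anti-HAV IgM, HBs antigen, HBc antibody, anti-HCV IgG and anti-HEV IgM, with a listing of new positives. If the Cut-off 1 outputs are already fixed, the same Core part table can go into the final analysis, since the current SAP was released before the final database lock.
3. Add HBs antibody to the screening table only, and leave it out of the definition of a new positive.
4. Reconcile the once-at-screening statement and Protocol 6.5.4.4 with Table 6-1, so that all three agree on when hepatitis serology is drawn.

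The cost is a wording change, one table and one listing. On the schedule as extracted no new samples are needed, and sample size, power and alpha are unchanged.
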